8.3.6 SERIOUS ADVERSE EVENT REPORTING

The study clinician will immediately report to the sponsor any serious adverse event, whether or not considered study intervention related, including those listed in the protocol and must include an assessment of whether there is a reasonable possibility that the study intervention caused the event. Study endpoints that are serious adverse events (e.g., all-cause mortality) must be reported in accordance with the protocol unless there is evidence suggesting a causal relationship between the study intervention and the event (e.g., death from anaphylaxis).

All serious adverse events (SAEs) will be followed until satisfactory resolution or until the site investigator deems the event to be chronic or the participant is stable.

The study sponsor will be responsible for notifying the Food and Drug Administration (FDA) of any unexpected fatal or life-threatening suspected adverse reaction as soon as possible, but in no case later than 7 calendar days after the sponsor's initial receipt of the information. In addition, the sponsor must notify FDA and all participating investigators in an Investigational New Drug (IND) safety report of potential serious risks, from clinical trials or any other source, as soon as possible, but in no case later than 15 calendar days after the sponsor determines that the information qualifies for reporting.

Any SAE identified by research personnel must be reported to the Principal Investigator with notification copied to the DSMB as soon as practicable, but within 24 hours.

• Initial reporting: IND application principal investigator/sponsor must report any suspected adverse reaction or adverse reaction to study treatment that is both serious and unexpected.

Unexpected fatal or life-threatening suspected adverse reactions represent especially important safety information and must be reported to FDA as soon as possible but no later than 7 calendar days following the sponsor's initial receipt of the information.

- Follow-up reporting: Any relevant additional information obtained by the sponsor that pertains to a previously submitted IND safety report must be submitted as a Follow-up IND Safety Report. Such report should be submitted without delay, as soon as the information is available but no later than 15 calendar days after the sponsor receives the information.
- All IND safety reports must be submitted on Form 3500A https://www.fda.gov/media/69876/download

8.3.7 REPORTING EVENTS TO PARTICIPANTS

Participants will be contacted as soon as practicable, via email, phone, or letter about any adverse events defined at "potentially related," "probably related," or "definitely related" to the study that are specifically related to the individual participant. A record of the communication will be recorded in the REDCap data collection system.

Upon completion of the study, participant will be emailed a summary of the study results written in layman terminology describing aggregate results of the study including a summary of adverse events and unanticipated problems believed to be related to the study.

8.3.8 EVENTS OF SPECIAL INTEREST

Any identified events not covered above, such as discovery of abnormal lab test results, study intervention overdose, or events that raise concern by the research clinician will be reported to the principal investigator and/or DSMB.

8.3.9 REPORTING OF PREGNANCY

If patient reports pregnancy during the study, they will be asked to discontinue the study intervention. Consent to follow the pregnancy outcome will be requested.

8.4 UNANTICIPATED PROBLEMS

8.4.1 DEFINITION OF UNANTICIPATED PROBLEMS (UP)

The Office for Human Research Protections (OHRP) considers unanticipated problems involving risks to participants or others to include, in general, any incident, experience, or outcome that meets all of the following criteria:

- Unexpected in terms of nature, severity, or frequency given (a) the research procedures that are described in the protocol-related documents, such as the Institutional Review Board (IRB)approved research protocol and informed consent document; and (b) the characteristics of the participant population being studied;
- Related or probably related to participation in the research ("probably related" means there is a reasonable probability that the incident, experience, or outcome may have been caused by the procedures involved in the research); and
- Suggests that the research places participants or others at a greater risk of harm (including physical, psychological, economic, or social harm) than was previously known or recognized.

8.4.2 UNANTICIPATED PROBLEM REPORTING

The investigator will report unanticipated problems (UPs) to the reviewing Institutional Review Board (IRB) and DSMB. The UP report will include the following information:

- Protocol identifying information: protocol title and number, PI's name, and the IRB project number
- A detailed description of the event, incident, experience, or outcome
- An explanation of the basis for determining that the event, incident, experience, or outcome represents an UP
- A description of any changes to the protocol or other corrective actions that have been taken or are proposed in response to the UP

To satisfy the requirement for prompt reporting, UPs will be reported using the following timeline:

- UPs that are serious adverse events (SAEs) will be reported to the IRB and DSMB as soon as practicable but within 48 hours of the investigator becoming aware of the event.
- Any other UP will be reported to the IRB and DSMB within 7 days of the investigator becoming aware of the problem.
- All UPs should be reported to appropriate institutional officials (as required by an institution's written reporting procedures), the supporting agency head (or designee), and the Office for Human Research Protections (OHRP) within 7 days of the IRB's receipt of the report of the problem from the investigator.
- https://www.hhs.gov/ohrp/regulations-and-policy/guidance/reviewing-unanticipated-problems/index.html

8.4.3 REPORTING UNANTICIPATED PROBLEMS TO PARTICIPANTS

Participants will be contacted as soon as practicable, via email, phone, or letter about any adverse events defined by study that are specifically related to the participant. A record of the communication will be recorded in the REDCap data collection system.

Upon completion of the study, participant will be emailed a summary of the study results written in layman terminology describing aggregate results of the study including a summary of adverse events and unanticipated problems believed to be related to the study.

9 STATISTICAL CONSIDERATIONS

9.1 STATISTICAL HYPOTHESES

• Primary Efficacy Endpoint(s):

Hospitalization (less frequent is better)

Null hypothesis: There is no difference between resveratrol and placebo with respect to the proportion of patients hospitalized or deceased within 21 days of randomization.

Alternative hypothesis: There is a difference between resveratrol and placebo with respect to the proportion of patients hospitalized or deceased within 21 days of randomization.

• Secondary Efficacy Endpoint(s):

ICU admission (less frequent is better)

Null hypothesis: There is no difference between resveratrol and placebo among patients who are hospitalized within 21 days of randomization with respect to the proportion of patients admitted to the ICU or deceased.

Alternative hypothesis: There is a difference between resveratrol and placebo among patients who are hospitalized within 21 days of randomization with respect to the proportion of patients admitted to the ICU or deceased.

Invasive ventilation (less frequent is better)

Null hypothesis: There is no difference between resveratrol and placebo among patients who are hospitalized within 21 days of randomization with respect to the proportion of patients receiving invasive ventilation or deceased.

Alternative hypothesis: There is a difference between resveratrol and placebo among patients who are hospitalized within 21 days of randomization with respect to the proportion of patients receiving invasive ventilation or deceased.

Extracorporeal membrane oxygenation (ECMO) (less frequent is better)

Null hypothesis: There is no difference between resveratrol and placebo among patients who are hospitalized within 21 days of randomization with respect to the proportion of patients receiving ECMO or deceased.

Alternative hypothesis: There is a difference between resveratrol and placebo among patients who are hospitalized within 21 days of randomization with respect to the proportion of patients receiving ECMO or deceased.

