3 OBJECTIVES AND ENDPOINTS			
OBJECTIVES	ENDPOINTS	JUSTIFICATION FOR ENDPOINTS	
Primary			
Reduction in hospitalization rates.	21-day hospitalization or death, defined as admission to any hospital for the treatment of COVID-19, or death, within 21 days of randomization for this study (date of randomization = day 0).	Based on reported typical course of illness for COVID-19 most patients will have declared their need for hospitalization in less than 21 days	
Secondary			
invasive ventilation rates, and ECMO usage rates admission to any intensive care unit (ICU) due to worsening symptoms of COVID-19, or death, among patients who are hospitalized within 21 days of randomization (date of randomization = day 0)		Based on reported typical course of illness for COVID-19 most patients will have declared their need for ICU admission/invasive ventilation/ECMO usage in less than 21 days	
Tertiary/Exploratory			
Reduction in morbidity and mortality	Reduction in signs and symptoms based on results of daily surveys. Will also observe mortality rates between groups.	There are mechanisms that would suggest improvements in morbidity and mortality, but this study will likely not have the statistical power to draw firm conclusions.	

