9.2 SAMPLE SIZE DETERMINATION

[figure not shown]
The maximum total number of randomized subjects is capped at 200 by FDA request. We present power analyses of the primary outcome measure (hospitalization) assuming multiple placebo arm

hospitalization rates and effect sizes, as well as for secondary outcome measures. No interim analyses for efficacy are planned, and none are included in the following power calculations.

The primary outcome measure is hospitalization within 21 days of randomization. We provide conservative power estimates by assuming a binary outcome with 5% non-informative loss to follow-up before 21 days. We anticipate this relatively low rate of loss because the endpoint is designed to be evaluable by chart review unless the subject withdraws consent. Hypotheses are as specified in the previous section, and the Z statistic for a two-proportion test is used. The primary Kaplan-Meier analysis will yield slightly better power by treating the outcomes of patients lost to follow-up as censored at the time of last follow-up.

The rate of hospitalization among confirmed cases of COVID-19 ranges between 21% in the 45-54 age bracket, up to 31% for patient's >85 (CDC, 2020). We assumed a mid-point hospitalization rate of 25% for the initial sample size calculation. To achieve 80% power at the 5% two-sided significance level with complete follow-up on 95 subjects per arm with two-sample proportion test, we require a 10% or lower hospitalization rate in the resveratrol arm, compared to a 25% rate in the placebo arm (estimated by power.prop.test, R statistical software). This corresponds to an odds ratio of 1 / 3.

The required resveratrol arm event rate for various placebo arm event rates are plotted in Figure 3. This curve applies to the power for all outcome measures, with lower rates of all secondary outcome events expected to be lower in both arms.

95 complete observations per arm, 80% power

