9.3 POPULATIONS FOR ANALYSES

- Intention-to-treat (ITT) population: all randomized participants.
- Safety population: all randomized participants who report taking at least one dose of their assigned medication.

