9.4 STATISTICAL ANALYSES

9.4.1 GENERAL APPROACH

Uncensored data will be summarized by percentages, means and standard deviations, or medians and ranges as appropriate for each variable's distribution. Data subject to censoring (e.g., hospitalization) will be summarized by Kaplan-Meier estimate.

Unless otherwise noted, all hypothesis tests will be two-sided and at the 5% significance level. Similarly, confidence intervals will be two-sided and at the 95% confidence level. Declarations of superiority will be declared if the corresponding hypothesis test is significant and the direction of the estimated treatment effect is favorable to resveratrol.

In addition to local hypothesis tests, we will use a multiple testing procedure to control the familywise Type I error at 5% for the primary and secondary endpoints together. The primary efficacy endpoint (hospitalization) will be tested at the 5% significance level; then, if the primary endpoint null hypothesis is rejected, the two secondary endpoints (ICU admission, invasive ventilation) will be tested via the Bonferroni-Holm procedure. No multiple testing adjustment will be made for exploratory or safety analyses.

Hospitalization, ICU admission, and invasive ventilation endpoints are composites that include death within 21 days of randomization.

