9.4.3 ANALYSIS OF THE SECONDARY ENDPOINT(S)

The secondary endpoints are ICU admission or death and invasive ventilation or death within 21 days after randomization, as established by medical record review. Outcomes of subjects who withdraw

consent or are otherwise lost to follow-up before 21 days will be considered missing. The intention to treat population for each endpoint will be used for analysis. Estimation and testing procedures will follow those of the primary efficacy endpoint.

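### Sections 3 and 9.1 define the secondary endpoints among hospitalized patients, section 9.4.3 among all randomized; neither is said to govern, and the hospitalized-only reading can reverse a real benefit.

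*Combined protocol and SAP*

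**What the plan says.** Section 3 defines the secondary outcome as an ICU, ventilation or ECMO event "or death, among patients who are hospitalized within 21 days of randomization (date of randomization = day 0". Section 9.1 repeats the condition in all six of its secondary null and alternative statements; the ICU pair reads "among patients who are hospitalized within 21 days of randomization with respect to the proportion of patients admitted to the ICU or deceased".

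Section 9.4.3 has no such condition: "The secondary endpoints are ICU admission or death and invasive ventilation or death within 21 days after randomization". It adds "The intention to treat population for each endpoint will be used for analysis", and section 9.3 gives one definition: "Intention-to-treat (ITT) population: all randomized participants".

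Section 9.2 takes its hypotheses from 9.1, yet says of a power curve drawn for 95 complete observations per arm: "This curve applies to the power for all outcome measures". Section 9.4.1 makes the endpoints composites with death by day 21 and specifies that, after a significant primary result, "the two secondary endpoints (ICU admission, invasive ventilation) will be tested via the Bonferroni-Holm procedure". ECMO appears in sections 3 and 9.1 but in neither 9.4.1 nor 9.4.3.

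**The concern.** The plan gives two denominators for the same endpoints and no order of precedence. Under 9.4.3 the comparison is randomized. Under sections 3 and 9.1 it is not: patients enter the denominator only by having the primary outcome event. If resveratrol prevents the milder admissions, those still admitted on resveratrol are a sicker group, and their ICU proportion rises even when fewer resveratrol patients reach the ICU. Deaths without admission also drop out, although 9.4.1 counts death in the composite.

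The hypothesis as written and the analysis as written can therefore give opposite answers from the same data, and an open denominator lets the choice be made after results are seen.

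**Working it through.** **Inputs from the plan (9.2).** 95 complete observations per arm, hospitalization 25% on placebo and 10% on resveratrol, two-sided 5%, stated power 80%, odds ratio 1/3.

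**The plan's own figure.** Two-proportion z test, pooled rate 0.175:

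power = Φ[(0.15·√95 − 1.96·√(2·0.175·0.825)) / √(0.25·0.75 + 0.10·0.90)] = Φ(0.776) = 78.1%, within 2 points of the stated 80%. The odds ratio is (0.10/0.90)/(0.25/0.75) = 1/3, as stated.

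**Size of the hospitalized-only comparison.** 95 × 0.25 = 23.75 and 95 × 0.10 = 9.5, or about 24 versus 10 patients. The 95-per-arm curve cannot apply to that.

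**Direction.** Let p be the risk of ICU or death among all randomized and h the risk of hospitalization, with events occurring only in hospitalized patients (a simplification). Then

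conditional risk ratio = (pR/hR)/(pP/hP) = (pR/pP) × (hP/hR) = 2.5 × (pR/pP) at 25% versus 10%.

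This equals 1 at pR/pP = 0.40. A true 60% reduction looks neutral, and any smaller one looks like harm. Example: 7.5% versus 4.5% among all randomized (a 40% reduction) becomes 7.5/25 = 30% versus 4.5/10 = 45% among hospitalized patients. No ICU rate is needed for the break-even point.

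**Frequency.** The documents give no ICU rate, so a 5% to 10% placebo risk of ICU or death among all randomized is assumed. There were 200,000 simulated trials per scenario (40,000 for Fisher exact), with an unadjusted pooled z test at 1.96, not the planned covariate-adjusted logistic model.

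| True effect; placebo risk | Hospitalized only: points to harm | Significant harm, z (Fisher) | All randomized: points to harm | Significant harm |
|---|---|---|---|---|
| 40% reduction; 5% | 70.1% | 10.7% (6.7%) | 18.3% | 0.36% |
| 40% reduction; 8% | 78.8% | 14.7% (10.4%) | 14.4% | 0.21% |
| 40% reduction; 10% | 84.1% | 18.4% (12.8%) | 12.2% | 0.16% |

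- **True halving (placebo 5%, 8%, 10%).** The hospitalized-only estimate points to harm in 59.5%, 64.8% and 68.6% of trials and is significant for harm in 6.3%, 7.4% and 8.1%. It detects the benefit in 0.6%, 0.7% and 0.7%, against 12.6%, 20.0% and 25.5% for all randomized.
- **No effect on ICU or death (5%, 8%).** Significant harm in 42.0% and 73.4%, against 2.2% and 2.5% for all randomized. The case stops at 8% because 10% would require every hospitalized resveratrol patient to have an event.
- **With the plan's gatekeeping.** For a true 40% reduction, the primary is significant and the secondary is significant for harm in 8.6%, 11.5% and 14.2% of trials; at Holm's first-step 2.5% level, in 5.4%, 7.3% and 9.0%. With no effect the figures are 32.8% and 57.0%, or 25.2% and 48.5% at the first step.

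**Sensitivity to the hospitalization effect.** The break-even ratio is hR/hP: 0.40 at 10%, 0.60 at 15%, 0.80 at 20%. At 25% versus 15%, a true 40% reduction looks neutral and a true halving points to harm in 33% to 38% of trials. At 25% versus 20%, a true 40% reduction points to harm in 24% to 32%.

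**The case against.** The best defense is that the operative text already points one way. Section 9.4.3 is the analysis section, it names the intention-to-treat population, and 9.2, 9.3, the death composite in 9.4.1 and the unconditioned synopsis all fit it. A logistic model with six terms is hardly workable on about 34 patients. The simulated harm then belongs to a reading the analysis section does not prescribe. This is a good reason to choose all randomized, but it does not remove the conflict. The hypotheses that the Holm procedure would test are written only in 9.1, 9.2 adopts them, and no rule of precedence is given.

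Three points of scale stand:

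- 25% versus 10% is the difference needed for 80% power, not a forecast, and the reversal weakens quickly as the hospitalization effect shrinks.
- The no-effect case at 8% is extreme: it puts 80% of hospitalized resveratrol patients in ICU or dead, against 32% on placebo.
- The bias runs against resveratrol, and 9.4.1 declares superiority only in the favorable direction, so false superiority claims are not inflated.

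Section 3 also limits ICU admission to worsening COVID-19, which 9.4.3 does not, so a correction should state that choice openly. ECMO is a separate gap and adds nothing to the denominator argument.

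**Conclusion.** The concern holds. The denominators conflict, nothing says which governs, and the version in sections 3 and 9.1 would mislead if followed because it conditions on the primary outcome. At the plan's own rates it multiplies the risk ratio by 2.5 and is expected to reverse any true reduction in ICU or death below 60%. The 2.5 and the 60% depend on 25% versus 10% and on events being confined to hospitalized patients. The trial frequencies rest further on assumed ICU-or-death risks and an unadjusted test, so they are illustrations. In general, reversal requires hospitalization to fall proportionately more than ICU or death. The primary endpoint and its type I error are untouched, and under 9.4.3 the secondary comparison is sound. This should be fixed before unblinding but does not threaten the trial's main result.

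**What to change.** Remove the restriction to hospitalized patients from section 3 and from every secondary hypothesis in 9.1. Define each endpoint as the proportion of all randomized participants with ICU admission or death, or with invasive ventilation or death, by day 21. Count survivors who were never admitted as having no event, and leave unknown outcomes missing, as 9.4.3 does. Say whether the COVID-19 cause limit on ICU admission in section 3 is kept; 9.4.3 has none. Report proportions among hospitalized patients descriptively, without a test. For ECMO, either label it exploratory or add it to the Holm family.

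The cost is wording only, with no new data. Percentages will look smaller on the larger denominator, and power stays low (13% to 26% for a true halving under the assumptions above). Adding ECMO would tighten Holm's first step from 5%/2 = 2.5% to 5%/3 = 1.67%.

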9.2 SAMPLE SIZE DETERMINATION

[figure not shown]
The maximum total number of randomized subjects is capped at 200 by FDA request. We present power analyses of the primary outcome measure (hospitalization) assuming multiple placebo arm

hospitalization rates and effect sizes, as well as for secondary outcome measures. No interim analyses for efficacy are planned, and none are included in the following power calculations.

The primary outcome measure is hospitalization within 21 days of randomization. We provide conservative power estimates by assuming a binary outcome with 5% non-informative loss to follow-up before 21 days. We anticipate this relatively low rate of loss because the endpoint is designed to be evaluable by chart review unless the subject withdraws consent. Hypotheses are as specified in the previous section, and the Z statistic for a two-proportion test is used. The primary Kaplan-Meier analysis will yield slightly better power by treating the outcomes of patients lost to follow-up as censored at the time of last follow-up.

The rate of hospitalization among confirmed cases of COVID-19 ranges between 21% in the 45-54 age bracket, up to 31% for patient's >85 (CDC, 2020). We assumed a mid-point hospitalization rate of 25% for the initial sample size calculation. To achieve 80% power at the 5% two-sided significance level with complete follow-up on 95 subjects per arm with two-sample proportion test, we require a 10% or lower hospitalization rate in the resveratrol arm, compared to a 25% rate in the placebo arm (estimated by power.prop.test, R statistical software). This corresponds to an odds ratio of 1 / 3.

The required resveratrol arm event rate for various placebo arm event rates are plotted in Figure 3. This curve applies to the power for all outcome measures, with lower rates of all secondary outcome events expected to be lower in both arms.

95 complete observations per arm, 80% power

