5 STUDY POPULATION

5.1 INCLUSION CRITERIA

The World Health Organization has categorized baseline severity (see table 1). For this study we will be targeting Mild COVID-19 based on their initial ability to be managed as an outpatient and known estimates for admission rates. Patients who test positive but are asymptomatic (such as being tested for contact tracing) will be excluded from the study as there are no defined estimated for admission rates for asymptomatic patients (patients who become symptomatic can be considered for enrollment).

Furthermore, patients age 45 and greater will be selected for this study due to their higher admission rates. In order to be able to detect a difference in treatment efficacy, a population with a higher admission rate is desirable in order keep the sample size (and its associated cost) down. Noting that, in general, the younger population is more social and may have higher rates of infection, but lower rates of admission including younger age patients in the study would likely skew the population to a low hospitalization rate with resultant difficulty detecting a difference between groups. In addition, in order to avoid unnecessary testing and exposure of healthcare workers to patients with COVID-19, pregnancy will be assessed via self-report of pregnancy potential and report of last menstrual period. The risk of pregnancy will be low in this age group.

Patient must test positive for SARS-CoV2 based on an FDA approved test. Due to low false positive rates and to minimize risk to healthcare providers, minimize the use of PPE and discomfort to the patient, repeat confirmatory testing will not be utilized.

- Outpatients in Central Ohio
- Age ≥45 years
- Mild COVID-19 based on WHO Baseline Severity Categorization (see Table 1)
- Symptom duration \leq 7 days
- Patient must have access to the internet or a smartphone to complete surveys
- English-speaking patients

Disease Severity	Description
SARS-CoV-2 Infection	Positive testing by standard reverse transcription polymerase chain
without Symptoms	reaction (RT-PCR) assay or equivalent test
	No Symptom
Mild COVID-19	Positive testing by standard RT-PCR assay or equivalent test
	• Symptoms of mild illness could include fever, cough, sore throat,
	malaise, headache, muscle pain, gastrointestinal symptoms,
	without shortness of breath or dyspnea
	No clinical signs indicative of Moderate, Severe, or Critical Severity

Table 1: Baseline Severity Categorization

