5.2 EXCLUSION CRITERIA

- Diagnosed or suspected cognitive impairment that would prevent the patient from cooperating with study procedures, as judged by the screening clinician.
- Asymptomatic patients (e.g. patients who were screened without symptoms but tested positive).
- Known history of cirrhosis, hepatic impairment, or Hepatitis C
- Known of history of renal impairment as measured by an eGFR of < 60 mL/min.
- Patients receiving chemotherapy or who are on chronic immunosuppressants.
- Allergy to grapes or rice.
- Co-morbidities with a high likelihood of hospitalization within 30 days (e.g., current cancer treatment, severe COPD or CHF)
- Currently pregnant

- Hospitalization
- Co-administration of "statins" and PDE-5 inhibitors must be withheld while on study treatment (see section 6.5).
- Due to concerns of patients taking immunosuppressants and drug interactions in medications with a narrow therapeutic index the use of the the following medications will be exclusionary (Blix, Viktil, Moger, & Reikvam, 2010) (Shaito, et al., 2020).

Immunosuppressants			
Generic Name Common Examples			

"Blood Thinners" / NOACs		
warfarin Coumadin		
rivaroxaban	Xarelto	
apixaban	Eliquis	
dabigatran	Pradaxa	

HIV Protease Inhibitors		
atazanavir	Reyataz	
darunavir	Prezista	
fosamprenavir	Lexiva	
indinavir	Crixivan	
lopinavir/ritonavir	Kaletra	
nelfinavir	Viracept	
ritonavir	Norvir	
saquinavir	Invirase	
tipranavir	Aptivus	
atazanavir/cobicistat	Evotaz	
darunavir/cobicistat	Prezcobix	

Immunosuppresants			
Janus Kinase Inhibitors			
tofacitinib	Xeljanz		
Calcineur	in Inhibitors		
cyclosporine	Neoral, Sandimmune, SangCya		
tacrolimus	Astagraf XL, Envarsus XR, Prograf		
mTOR inhibitors			
sirolimus Rapamune			
everolimus	Afinitor, Zortress		
IMDH inhibitors			
azathioprine Azasan, Imuran			
leflunomide Arava			
mycophenolate CellCept, Myfortic			
Bio	Biologics		

abatacept	Orencia	
adalimumab	Humira	
anakinra	Kineret	
certolizumab	Cimzia	
etanercept	Enbrel	
golimumab	Simponi	
infliximab	Remicade	
ixekizumab	Taltz	
natalizumab	Tysabri	
rituximab	Rituxan	
secukinumab	Cosentyx	
tocilizumab	Actemra	
ustekinumab	Stelara	
vedolizumab	Entyvio	
Monoclonal Antibodies		
basiliximab	Simulect	
daclizumab	Zinbryta	
other		
hydroxychloroquine	Plaquenil	
chloroquine	Aralen	

Seizure medications	
carbamazepine	Tegretol
phenobarbital	Luminol
phenytoin	Dilantin
valproate	Depakote

Cardiac medications	
amiodarone	Cardarone, Pacerone
digoxin	Lanoxin
flecainide	Tambocor
sotalol	Betapace

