8.2 SAFETY AND OTHER ASSESSMENTS

Safety Monitoring. This study while only be initiated after approval by Mt Carmel Health System's Research Advisory Review Committee (RARC), Institutional Review Board (IRB), and the Food and Drug Administration (FDA).

An independent Data and Safety Monitoring Board (DSMB) will been convened to assess the progress of a clinical study, the safety data, and critical efficacy endpoints (if appropriate) and provide recommendations. The members of the DSMB serve in an individual capacity and provide their expertise and recommendations. The DSMB will review cumulative study data to evaluate safety, study conduct, and scientific validity and data integrity of the study. The charter for the DSMB was developed by the Trinity Health research department.

In addition to daily self-assessment via survey, participants will be provided with a consumer grade finger pulse oximeter. They will be instructed to (at minimum) record their resting pulse oximeter reading of pulse rate and oxygen saturation each evening. Patients will be instructed to seek medical attention for best resting oxygen saturation (SaO2) <94% on room air, or resting heart rate \geq 90 beats per minute. Patients will be cautioned faulty readings and techniques for accurate readings. Consumer grade pulse oximeters report an accuracy of +/- 2%.

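### Do the 25% placebo rate in 9.2 and the futility probabilities in 9.4.6 need reworking because the trial enrolls only mild outpatients?

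*Combined protocol and SAP*

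**What the plan says.** Section 9.2 starts from CDC figures by age: "The rate of hospitalization among confirmed cases of COVID-19 ranges between 21% in the 45-54 age bracket", up to 31% above age 85. It continues: "We assumed a mid-point hospitalization rate of 25% for the initial sample size calculation". One example is worked in numbers. With 95 evaluable patients per arm, two-sided 5% and 80% power, the resveratrol rate must be 10% or lower against 25% on placebo, an odds ratio of 1/3. For other rates the section refers to a plot: "The required resveratrol arm event rate for various placebo arm event rates are plotted in Figure 3". The total of 200 is a cap set at FDA request.

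Section 9.4.6 places one interim analysis after 100 patients, with Hwang-Shih-DeCani bounds (gamma = -4). It gives the probability of declaring futility as 3%, 55% and 75% for resveratrol rates of 10%, 25% and 30%. These are stated to hold for a binding bound and a 25% placebo rate. No other placebo rate is shown there.

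The enrolled population is narrower than confirmed cases at large. Section 5.1 describes the trial as "targeting Mild COVID-19 based on their initial ability to be managed as an outpatient and known estimates for admission rates" and defines mild disease as "without shortness of breath or dyspnea". Section 5.2 excludes "Co-morbidities with a high likelihood of hospitalization within 30 days (e.g., current cancer treatment, severe COPD or CHF").

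**The concern.** Moderate, severe and critical patients, and those already in hospital, contribute admissions to a rate among all confirmed cases. This trial screens them out. Section 5.1 says admission rates for mild disease are known, and drops asymptomatic positives because they "will be excluded from the study as there are no defined estimated for admission rates for asymptomatic patients". Yet no rate for mild outpatients appears in the documents. A reader may fairly suspect that 25% is too high.

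If it is, two things follow when the relative effect is held at the planned size. Power at 95 per arm falls, so a non-significant final result says less. The chance that an effective treatment crosses the lower bound at the interim analysis also rises above 3%, and a crossing suspends enrollment. Readers of 9.4.6 have only the 25% figures to go by.

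**Working it through.** **Inputs.** From 9.2: placebo 25%, resveratrol 10%, 95 per arm, two-sided 5%, source range 21% to 31%. From 9.4.6: gamma = -4, total Type II error 20%, one-sided Type I error 2.5%, interim at 100 of 200 patients (taken as 50 per arm, information fraction 0.5). Assumed, because the documents give no value: placebo rates of 15%, 10% and 5%, and a constant odds ratio of 1/3.

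**Step 1: the plan's power.** The odds ratio is (0.10/0.90)/(0.25/0.75) = 1/3, as stated. With mean rate 0.175,

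z = [√95 × 0.15 − 1.96 × √(2 × 0.175 × 0.825)] / √(0.25 × 0.75 + 0.10 × 0.90) = (1.462 − 1.053)/0.527 = 0.776,

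so power is 78.1%. Exactly 80% needs 9.7% on resveratrol, which rounds to the stated 10%.

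**Step 2: the futility bound.** Type II error spent at half information is 0.20 × (e² − 1)/(e⁴ − 1) = 0.20 × 6.389/53.598 = 0.0238. Solving the two-look binding design gives a final drift of 2.821 and a lower interim bound of z = 0.015. The inputs are the two error rates, gamma and the timing. None is an event rate, so the bound is the same whatever the placebo rate turns out to be.

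With 50 per arm, equal counts give z = 0 and cross. A one-event difference in favor of resveratrol gives z of at least 0.02/0.10 = 0.2 and does not. The rule is therefore: resveratrol events ≥ placebo events.

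**Step 3: the plan's futility probabilities.** P(futility) = Σₓ P(placebo events = x) × P(resveratrol events ≥ x), both binomial with n = 50. At placebo 25% and resveratrol 10%, 25% and 30% this gives 2.9%, 54.6% and 75.0%, against the stated 3%, 55% and 75%. If ties do not cross, it gives 1.5%, 45.4% and 67.4%, so the plan's figures match the version with ties crossing.

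**Step 4: other placebo rates.** Resveratrol odds are one third of placebo odds. At 10%, for example, (0.10/0.90)/3 = 0.0370, a rate of 3.6%.

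| Placebo | Resveratrol | Power, 95 per arm | False futility, ties cross | False futility, ties do not cross | Futility, no effect (ties cross) |
|---|---|---|---|---|---|
| 31% | 13.0% | 85.4% | 1.8% | 0.9% | 54.3% |
| 25% | 10.0% | 78.1% | 2.9% | 1.5% | 54.6% |
| 21% | 8.1% | 71.3% | 4.2% | 2.1% | 54.9% |
| 15% (assumed) | 5.6% | 57.4% | 7.6% | 3.8% | 55.6% |
| 10% (assumed) | 3.6% | 42.1% | 13.4% | 6.2% | 56.7% |
| 5% (assumed) | 1.7% | 23.9% | 26.4% | 10.5% | 59.4% |

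Holding the planned relative risk of 0.4 instead, false futility with ties crossing is 4.6%, 9.0%, 15.9% and 29.5% at 21%, 15%, 10% and 5%. If the effect is enlarged to keep 80% power, false futility stays low (2.6% at 21%, 2.2% at 10%), but at a 10% placebo rate that requires 0.8% on resveratrol.

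**The case for a change.** The strongest case for a change is that the eligibility criteria all but guarantee a rate below that of confirmed cases at large, and that the remedy is one small table. At a 10% placebo rate, a treatment with the planned odds ratio would cross the lower bound 13% of the time rather than 3%. Power would be 42%, so a completed trial would miss the effect more often than find it. Figure 3, as described, covers the effect required at the final analysis and says nothing about the interim.

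Part of this stands. The source of the 25% does not match the enrolled patients, and 9.4.6 shows one placebo rate only. But the size of any shortfall is not in the documents, and some features push the rate up: asymptomatic positives are excluded, patients with heart, lung or neurologic disease remain as a risk group in 9.4.7, and an oximeter is supplied (section 8.2: "Patients will be instructed to seek medical attention for best resting oxygen saturation" under a set threshold). Whether admissions for any cause count is unsettled between section 3 and 9.4.2, so that cannot be relied on in either direction.

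The consequence is also milder than a wrongly stopped trial. Enrollment is already paused at 100 patients until the interim analysis is done. A crossing leads to an ad hoc DSMB review and then an IRB and FDA decision on resuming. Under 10.1.6 the DSMB sees safety and efficacy data by arm, so it will know the actual event counts.

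**Conclusion.** No change is called for. Every stated figure reproduces, and 9.4.6 declares the placebo rate on which its probabilities depend. Section 9.2 treats 25% as a starting assumption and presents other rates in Figure 3, which is absent from the extracted text but not from the plan. Across the only range the documents give, false futility is 1.8% to 4.2%, in practice the stated 3%. The larger values need assumed rates of 15% or less and a constant odds ratio of 1/3. At 10% and 5% more than half of each is the probability of exactly tied counts.

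The bound does not use the 25%, the sample size is capped from outside, and the proof-of-concept aim is unaffected. A wider set of planning figures would be informative, but it would alter no boundary, trigger, analysis or sample size. If the observed placebo rate is low, the wide confidence interval around the treatment effect will show it, and the analysts can say so when reporting.

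The conclusion rests on 50 per arm at the interim analysis and on an unadjusted comparison of counts. Section 9.4.6 does not name the interim statistic, and a covariate-adjusted one would treat ties somewhat differently.
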